Key secondary objectives will be to compare the effect of intravenous dexamethasone (combined dose DXMT), relative to placebo, on the following outcome measures:

- Postoperative pain intensity during rest at 24 hours. Pain intensity is assessed using the visual analogue scale (VAS) (0-100mm).
- Postoperative pain intensity during activity at 24 hours. Pain is evaluated under the timed-up-and-go (TUG) procedure. Pain intensity is assessed using the visual analogue scale (VAS) (0-100mm).
- Postoperative pain intensity during rest at 48 hours. Pain intensity is assessed using the visual analogue scale (VAS) (0-100mm).
- Postoperative pain intensity during activity at 48 hours. Pain is evaluated under the timed-up-and-go (TUG) procedure. Pain intensity is assessed using the visual analogue scale (VAS) (0-100mm).

- Cumulated postoperative morphine consumption from 48 hours until day 14 post operation [Time Frame: 48 hours - day 14 postoperatively] Morphine consumption in milligrams after the operation.
- Postoperative nausea and vomiting [Time Frame: 24 hours postoperatively] Nausea and vomiting are evaluated using a 4 point scale: none, mild, moderate, severe
- Postoperative nausea and vomiting [Time Frame: 48 hours postoperatively] Nausea and vomiting are evaluated using a 4 point scale: none, mild, moderate, severe
- Antiemetic consumption [Time Frame: 0-48 hours postoperatively] Evaluation of cumulated antiemetic consumption in mg and drug will be assessed.
- Timed up and go test [Time Frame: 24 hours postoperatively] Is assessed from; the time that the participant takes to rise from a chair, walk three meters, turn around, walk back to the chair, and sit down.
- Timed up and go test [Time Frame: 48 hours postoperatively] Is assessed from; the time that the participant takes to rise from a chair, walk three meters, turn around, walk back to the chair, and sit down.

Secondary objectives will be outlined to include comparison of the three intervention groups in different setups: If statistically significant difference between placebo and the combined groups of DXMT is found, the two DXMT groups will be compared afterwards.

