The CONSORT flowchart will comprise number of patients screened, excluded (with reasons) eligible for inclusion in the trial, randomised, receiving their allocated treatment, withdrawals (with reasons), and lost to follow-up (with reasons), included in the ITT analysis, included in per protocol analysis, and included in as treated analysis. The CONSORT flowchart is depicted in **Figure 1**.

Withdrawal / follow-up

The level of consent withdrawal will be classified as the following two options: 1) consent to continue follow-up and data collection and 2) complete withdrawal with no further follow-up and data collection. Timing of withdrawal and loss to follow-up will be presented in the CONSORT flowchart with numbers and reasons for withdrawal and/or loss to follow-up. Furthermore, the number (with reasons) of loss to follow-up during the course of the trial will be summarised by treatment group.

Missing data and sensitivity analyses

Statistical methods to handle missing data: Loss to follow-up (and missing data for various reasons) is hard to avoid in randomised trials. We will apply the analysis framework suggested by White et al for “ITT analyses” that depends on making plausible assumptions about the missing data and including all participants in sensitivity analyses:

1. Attempt to follow up all randomised participants, even if they withdraw from allocated treatment
2. Perform a main analysis of all observed data that are valid under a plausible assumption about the missing data (i.e., ‘Missing At Random’ [MAR], applying multiple imputation to handle missing outcome data)
3. Perform sensitivity analyses to explore the effect of departures from the assumption made in the main analysis (i.e., using both the Per Protocol population as well as the simplistic non-responder imputation).
4. Account for all randomised participants, at least in the sensitivity analyses.

The evaluability assessment of each participant in the statistical analyses will be performed before the code is revealed. Excluded participants and missing, unused or false data will be described.

Protocol deviations will be reported (defined as a failure to adhere to the protocol such as the wrong intervention being administered, incorrect data being collected and documented, errors in applying inclusion/exclusion criteria or missed follow-up visits). These will be defined as major or minor.

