* Will be reported for each group as Least Squares Means with Standard Errors while the Difference between them will be reported with 95% Confidence intervals. Continuous endpoints will be analyzed using an analysis of covariance (ANCOVA) model with randomized treatment, stratification groups, and baseline outcome value as covariate. Missing data will be imputed from all retrieved patients and the results will be combined using Rubin's rules. Categorical endpoints will be analyzed by logistical regression.

Table 3. Reporting of Harms

Characteristic	Placebo group	DXMT/placebo	DXMT/DXMT
Serious adverse events (SAE), up to 8 weeks after operation, no. (%)			
Deep infection, no. (%)			
Revision due to acetabular/femoral fracture, no. (%)			
Deep venous thrombosis/pulmonary embolism, no. (%)			
Nerve injury, no. (%)			
Death, no. (%)			

* Will be reported as numbers and percentages (no. [%])

Table 4. Optional Exploratory Analyses Primary and Ten Key Secondary Outcomes in the ITT Population

Characteristic	Placebo (N=??)	DXMT/placebo (N=??)	DXMT/DXMT (N=??)	Difference: Double vs Single Dose (95% CI)
Cumulated postoperative morphine consumption, up to 48 hours - mg				
*Postoperative pain intensity after 24 hours - VAS, at rest (points 0 - 100)				
*Postoperative pain intensity after 24 hours - VAS, during activity (points 0 - 100)				
*Postoperative pain intensity after 48 hours - VAS, at rest (points 0 - 100)				
*Postoperative pain intensity after 48 hours - VAS, during activity (points 0 - 100)				
*Cumulated postop. morphine from 48 hrs to 14 days - mg				
*Postop. nausea and vomiting at 24 hrs - (points 0 – 3)				
*Postop. nausea and vomiting at 48 hrs - (points 0 – 3)				
*Postop. antiemetic consumption at 48 hrs – cumulated mg				
*Timed up and go test 24 hours - sec				
*Timed up and go test 48 hours - sec				

* Will be reported for each group as Least Squares Means with Standard Errors while the Difference between them will be reported with 95% Confidence intervals. Continuous endpoints will be analyzed using an analysis of covariance (ANCOVA) model with randomized treatment, stratification groups, and baseline outcome value as covariate. Missing data will be imputed from all retrieved patients and the results will be combined using Rubin's rules. Categorical endpoints will be analyzed by logistical regression (reported as an Odds Ratio with 95% confidence interval).

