Appendix Table 1. Sensitivity Analysis Table, Primary and Ten Key Secondary Outcomes in the Per Protocol Population

Characteristic	Placebo group (N=??)	DXMT groups (N=??)	Difference (95% CI)
Cumulated postoperative morphine consumption, up to 48 hours - mg			
*Postoperative pain intensity after 24 hours - VAS, at rest (points 0 - 100)			
*Postoperative pain intensity after 24 hours - VAS, during activity (points 0 - 100)			
*Postoperative pain intensity after 48 hours - VAS, at rest (points 0 - 100)			
Postoperative pain intensity after 48 hours - VAS, during activity (points 0 - 100)			
*Cumulated postop. morphine from 48 hrs to 14 days - mg			
*Postop. nausea and vomiting at 24 hrs - (points 0 – 3)			
*Postop. nausea and vomiting at 48 hrs - (points 0 – 3)			
*Postop. antiemetic consumption at 48 hrs – cumulated mg			
*Timed up and go test 24 hours - sec			
*Timed up and go test 48 hours - sec			

The per protocol population will be defined as participants who were (i) randomized, AND (ii) had the intended prescription (randomly allocated intervention), AND (iii) had a successfully measured primary endpoint. Will be reported for each group as Least Squares Means with Standard Errors while the Difference between them will be reported with 95% Confidence intervals. Continuous endpoints will be analyzed using an analysis of covariance (ANCOVA) model with randomized treatment, stratification groups, and baseline outcome value as covariate. Missing data will be imputed from all retrieved patients and the results will be combined using Rubin's rules. Categorical endpoints will be analyzed by logistical regression (reported as an Odds Ratio with 95% confidence interval).

Appendix Table 2. Sensitivity Analysis Table, Primary and Ten Key Secondary Outcomes in the Non-Responder Population

Characteristic	Placebo group (N=??)	DXMT groups (N=??)	Difference (95% CI)
Cumulated postoperative morphine consumption, up to 48 hours - mg			
*Postoperative pain intensity after 24 hours - VAS, at rest (points 0 - 100)			
*Postoperative pain intensity after 24 hours - VAS, during activity (points 0 - 100)			
*Postoperative pain intensity after 48 hours - VAS, at rest (points 0 - 100)			
*Postoperative pain intensity after 48 hours - VAS, during activity (points 0 - 100)			
*Cumulated postop. morphine from 48 hrs to 14 days - mg			
*Postop. nausea and vomiting at 24 hrs - (points 0 – 3)			
*Postop. nausea and vomiting at 48 hrs - (points 0 – 3)			

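### The SAP has no rule for patients unable to perform the timed-up-and-go test: its one missing-at-random imputation rule can bias four of the ten key secondary outcomes, and the planned sensitivity analyses do not repair this

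*SAP*

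**What the plan says.** Under Objectives, TUG is a completion time: "the time that the participant takes to rise from a chair, walk three meters, turn around", then back to the chair. Pain during activity has no separate assessment: "Pain is evaluated under the timed-up-and-go (TUG) procedure". Both are taken at 24 and 48 hours, which makes four of the ten key secondary outcomes in Table 2.

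Under Missing data and sensitivity analyses, the main analysis assumes missingness at random, "applying multiple imputation to handle missing outcome data". The Table 2 footnote adds: "Missing data will be imputed from all retrieved patients and the results will be combined using Rubin's rules". The imputation model is not described further.

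Departures from that assumption are to be explored "using both the Per Protocol population as well as the simplistic non-responder imputation". For data, the per protocol set requires only that the participant "had a successfully measured primary endpoint". The non-responder results go into Appendix Table 2, titled "Sensitivity Analysis Table, Primary and Ten Key Secondary Outcomes in the Non-Responder Population". Its rows include all four TUG-based outcomes, and its footnote repeats the imputation sentence of Table 2.

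**The concern.** A patient who cannot rise and walk a day or two after a pelvic osteotomy has neither a TUG time nor a pain score during TUG at that visit. The likely reasons are pain, nausea or poor mobility, which are the very things being measured or are close to them. The SAP's introduction itself describes pain and nausea as a major challenge after this operation, so inability is foreseeable. For these outcomes missingness at random is doubtful, although the SAP's framework rests on a plausible assumption about the missing data.

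The SAP has no category, value or rank for inability. If inability is entered as missing, the plan gives these patients values modelled on patients who managed the test. Any treatment benefit or harm that shows as a difference in the number able to do the test is then partly lost from, or distorts, the comparison.

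**Working it through.** **The plan's own figures.** The SAP gives no effect size, SD or missing share for TUG or activity pain. Its sample-size figures concern morphine and reproduce. For 2:1 allocation, n per control arm = 1.5 × (1.960 + 1.282)² × (40/30)² = 28.0. Since 56 vs 28 gives 89.3% power by the noncentral t and 58 vs 29 gives 90.3%, the total is 87. Power is 80.8% for 44 vs 22 and 81.5% for 30 vs 30. Nothing below changes these figures.

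**Illustration (all inputs assumed).** Take a latent outcome in SD units, higher being worse: placebo N(0, 1), dexamethasone N(−0.5, 1), so the true effect is 0.50 SD. The worst patients in each arm, above cut-off c, cannot do the test. With λ(z) = φ(z)/Φ(z):

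- the mean of placebo patients able to do the test is −λ(c_P)
- the mean of dexamethasone patients able to do the test is −0.5 − λ(c_D), with c_D measured from that arm's own mean
- imputation with arm in the model and no auxiliary variable targets 0.5 − λ(c_P) + λ(c_D)

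*Same cut-off in both arms, so inability is commoner on placebo (c_D = c_P + 0.5):*

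| Unable, placebo | Unable, dexamethasone | λ(c_P) | λ(c_D) | Estimate, no auxiliary | Estimate, auxiliary correlated 0.7 |
|---|---|---|---|---|---|
| 5% | 1.6% | 0.109 | 0.041 | 0.43 | 0.46 |
| 10% | 3.7% | 0.195 | 0.085 | 0.39 | 0.44 |
| 20% | 9.0% | 0.350 | 0.178 | 0.33 | 0.40 |
| 30% | 15.3% | 0.497 | 0.279 | 0.28 | 0.36 |

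Without an auxiliary the loss is 14% to 44%. The last column comes from a simulation of 400,000 patients per arm, which also reproduces the formula results to two decimals in this table.

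*Equal share unable in both arms (c_P = c_D).* The λ terms cancel, so the estimate is 0.50 with arm in the imputation model. Without arm and without auxiliaries, a share f is filled from a common mean, so the estimate is 0.50 × (1 − f): 0.475, 0.45, 0.40 and 0.35 at f = 5%, 10%, 20% and 30%.

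*Twice as many unable on dexamethasone, at 5%, 10%, 20% and 30% (placebo half of that).* With arm in the model and no auxiliary:

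- 5%: 0.5 − 0.060 + 0.109 = 0.55
- 10%: 0.5 − 0.109 + 0.195 = 0.59
- 20%: 0.5 − 0.195 + 0.350 = 0.66 (0.655)
- 30%: 0.5 − 0.274 + 0.497 = 0.72

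The effect is inflated.

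**The same on the pain scale (assumed means 60 vs 45 mm, SD 25, true difference 15 mm).**

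| Cut-off | Unable, placebo vs dexamethasone | Means of patients able to do the test | Difference | Loss |
|---|---|---|---|---|
| 80 mm | 21.2% vs 8.1% | 50.81 vs 40.93 | 9.88 mm | 34% |
| 90 mm | 11.5% vs 3.6% | 54.51 vs 42.95 | 11.56 mm | 23% |
| 100 mm | 5.5% vs 1.4% | 57.07 vs 44.10 | 12.97 mm | 14% |

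**Do the sensitivity analyses help?** Per protocol conditions on the morphine endpoint and on treatment received. A patient in that set without a TUG value is imputed as before, since the Appendix Table 1 footnote carries the same sentence. Non-responder imputation needs a value for a non-responder; none is given for a time or a VAS score, and the footnote to its own table prescribes the main multiple imputation again. As written, neither explores the departure from missingness at random that matters here.

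**The case against.** Four points on the other side have weight.

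- *Inability may not be coded as missing.* A protocol or case report form may assign a maximum time, or score pain at the attempt. That stands, and the conclusion is therefore conditional. How a missing outcome is analysed is nonetheless the SAP's task, and it states one rule without exception.
- *The direction is not known.* A reader might infer that the plan shrinks the effect. That follows only if inability is commoner on placebo, which is what one would expect if the drug works, or if arm is left out of the imputation model. The document gives no missingness by arm, and the opposite pattern inflates the effect. Likewise, the 34% loss belongs to one severe assumed scenario with a sharp cut-off and no auxiliaries; an auxiliary correlated 0.7 brings it to 21% (11.9 mm).
- *The arms are not said to be pooled.* A reader might take "Missing data will be imputed from all retrieved patients" to mean imputation regardless of arm. The phrase names a data source and does not say that arm is omitted; the analysis model in the same footnote includes randomised treatment. It is an ambiguity to remove, not a stated error.
- *The imputation model is open.* Rest pain, morphine use and nausea do not require standing and could serve as auxiliaries. They would reduce the bias but, in the illustration, not remove it, and the SAP names none.

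It is also fair that replacing the ANCOVA by a rank test as the main analysis would change the declared estimand. The fix below does not do so.

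**Conclusion.** The concern holds as a gap with possible bias in either direction. Four of the ten key secondary outcomes cannot be observed in patients unable to do the test, the only stated rule treats such values as missing at random, and the two sensitivity analyses leave this untouched. The size rests on assumptions that the SAP cannot supply: a true effect of 0.50 SD, inability fixed by the outcome itself, and 5% to 30% unable in the arm with more missing values. On these, with arm in the model and no auxiliary, the estimate ranges from 0.28 SD (inability commoner on placebo) through 0.50 SD (equal shares) to about 0.72 SD (commoner on dexamethasone). If very few patients are unable, the matter is small. The primary outcome does not depend on standing and is not touched. This should be changed, but it does not threaten the main conclusion of the trial.

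**What to change.** Before unblinding:

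1. Classify each missing TUG time and activity-pain score as unable because of the patient's condition, or missing for another reason. This fits the evaluability assessment that the SAP already schedules before the code is revealed. Report the number unable per arm at 24 and 48 hours.
2. Keep the ANCOVA as the main analysis. Specify the imputation model with randomised arm and the observed auxiliaries (rest pain, morphine use, nausea and vomiting), and reword the footnotes to Tables 2 and 4 and Appendix Table 1 accordingly.
3. For these four outcomes, replace the non-responder imputation in Appendix Table 2 with a prespecified analysis that gives patients unable to perform the worst rank, or a stated worst value. Impute only what is missing for other reasons, and correct that table's footnote.

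The cost is one blinded data check and some SAP wording. A worst-rank result is not expressed in millimetres or seconds, so it stands beside the least squares mean difference and does not replace it.
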